# 2.5.2 Amgen Study 20110100

Amgen Study 20110100 is a phase 2, multicenter, open-label, single-arm study. In Study 20110100 cinacalcet is being evaluated in pediatric subjects enrolled between the ages of 28 days and < 6 years, with SHPT and CKD receiving either hemodialysis or peritoneal dialysis. The expected treatment period in 20110100 is 24 weeks of daily oral administration of cinacalcet in addition to SOC with a 2-week safety follow-up period. Subjects who are eligible for and enroll in the 20140159 extension study will do so at the completion of the week 26 End of Study visit or at Study 20110100 termination and within 7 days of day 1 of 20140159 unless there is an administrative delay. For subjects enrolled in the 20140159 extension study at the time of 20110100 study termination, the 2-week safety follow-up period in 20110100 will not apply for these subjects and the EOS procedures for an individual subject will occur at the time as the EOIP visit for subjects enrolling in Study 20140159.

# 2.6 Rationale

Cinacalcet has been shown to be safe and efficacious in treating adult CKD patients with SHPT by controlling iPTH, calcium, and phosphorus. The current study is an extension of Amgen studies 20130356 and 20110100 designed to assess the long-term safety and tolerability of cinacalcet in pediatric CKD subjects.

# 2.7 Clinical Hypotheses

A formal hypothesis does not apply for the study. The long-term safety and tolerability of cinacalcet in pediatric subjects will be characterized in this study.

Page 17 of 79

Page 18 of 79

# 3. EXPERIMENTAL PLAN

#### 3.1 Study Design

This is a phase 3, 32-week, multicenter, single-arm, extension study designed to characterize the long-term safety and tolerability of cinacalcet in pediatric subjects. Subjects will remain on cinacalcet treatment for 28 weeks after enrollment or until the time of renal transplant or parathyroidectomy, whichever occurs first. The treatment period is followed by a 4-week safety follow-up period.

The overall study design is described by a **Study Design and Treatment Schema** at the end of the protocol synopsis section.

The study endpoints are defined in Section 10.1.1.

# 3.1.1 Subjects From Study 20130356

Eligible subjects will complete the 20-week treatment period in Study 20130356, or reach Study 20130356 termination and either continue, restart, or start cinacalcet treatment in this study. Eligible subjects will not complete the safety follow-up period in Study 20130356, beginning the extension study at the 20130356 EOIP study visit. The EOIP visit in Study 20130356 and day 1 in Study 20140159 will be the same visit unless there is an administrative delay. Eligible subjects will complete day 1 of 20140159 assessments (Section 7.1) and confirm eligibility in the interactive voice response (IVR) system before dispensing IP on day 1.

Eligible subjects from 20130356 who were randomized to the SOC arm in Study 20130356 will begin cinacalcet treatment on day 1 in Study 20140159 if their iPTH is  $\geq$  300 pg/mL and cCa is  $\geq$  8.8 mg/dL during screening in Study 20140159. Eligible subjects from the cinacalcet arm in 20130356 will continue cinacalcet treatment on day 1 if their iPTH is  $\geq$  150 pg/mL and cCa is  $\geq$  8.4 mg/dL during screening in Study 20140159. If IP has been withheld or missed for > 14 days at the time of day 1 of Study 20140159, the subject will resume dosing at the starting dose level once all restart criteria are met.

Cinacalcet dosing will follow the dose titration, dose withhold, and restarting rules defined in Section 6.2.3.

Subjects will complete day 1 assessments (Section 7.1) and confirm eligibility in IVR system prior to dispensing IP on day 1.

All subjects from 20130356 will be eligible to titrate the cinacalcet dose at monthly titration visits (beginning at week 4) to a maximum dose of 2.5 mg/kg/day based on the subject's dry weight at day 1 in Study 20140159, not to exceed a dose of 180 mg/day.

Page 19 of 79

# 3.1.2 Subjects From Study 20110100

Eligible subjects will complete the End of Study visit or early termination visit for Study 20110100 and continue or restart cinacalcet treatment in this study on day 1 based on dosing instructions outlined in Section 6.2.3. Eligible subjects completing the full treatment period in Study 20110100 will be screened during the safety follow-up period in Study 20110100 and will be required to have their 20140159 day 1 visit and their 20110100 week 26 End of Study visit at the same visit. Eligible subjects who reach Study 20110100 termination before week 26 will not complete the safety follow-up period in Study 20110100, beginning the 20140159 extension study at the 20110100 early termination visit. The early termination/EOS visit in Study 20110100 and day 1 in Study 20140159 will be the same visit unless there is an administrative delay.

Subjects will complete day 1 assessments (Section 7.1) and confirm eligibility in IVR system before being dispensed IP on day 1.

Eligible subjects will continue cinacalcet treatment on day 1 based on their dry weight at the time of enrollment in 20140159 study if their iPTH is  $\geq$  150 pg/mL and cCa is  $\geq$  8.8 mg/dL (age < 2 years of age) or cCa is  $\geq$  8.4 mg/dL (age is  $\geq$  2 years of age) during screening in Study 20140159. If IP has been withheld or missed for > 14 days at the time of day 1 of Study 20140159, the subject will resume dosing at the starting dose level based on dry weight at the time of enrollment once all restart criteria are met. Cinacalcet dosing will follow the dose titration, dose withhold, and restarting rules defined in Section 6.2.3.1.2.

All subjects from 20110100 will be eligible to titrate the cinacalcet dose at monthly titration visits (beginning at week 4) to a maximum dose of 2.5 mg/kg/day based on the subject's dry weight at day 1 in Study 20140159, not to exceed a dose of 60 mg/day.

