#### During the 20140159 study:

Weekly monitoring of ionized calcium will be required for all subjects through the end of the treatment period, week 28.

Cinacalcet doses will be calculated by the site staff and confirmed by the interactive voice response/interactive web response (IVR/IWR) system following the titration tables in Section 6. The titration tables are based on cCa and iPTH values from the central laboratory collected one week before dose titration. Final dose assignment will be based on the ionized calcium obtained

Page 5 of 79

CONFIDENTIAL

on the day of titration. An assessment of symptomatic hypocalcemia will also be performed on the day of titration. Additional weekly dose adjustments for safety are permitted as described in Section **6.2.3.1**. The maximum dose assigned for all subjects will be 2.5 mg/kg/day (based on dry weight at day 1 in Study 20140159) not to exceed a dose of 180 mg/day for subjects from 20130356 and 60 mg/day for subjects from 20110100.

For all subjects, it is recommended that the vitamin D sterols, calcium supplementation, and phosphate binders be administered as appropriate per individual clinical practice. The use of medications that may prolong the corrected QT (QTc) interval (eg, ondansetron, albuterol), CYP3A4 inhibitors (eg, erythromycin, clarithromycin, ketoconazole, itraconazole), CYP2D6 substrates (eg, flecainide, propafenone, metoprolol, desipramine, nortriptyline, clomipramine), and commercial cinacalcet during the course of the trial are prohibited while the subject is receiving investigational product.

Serious adverse events will be collected from the date of the first dose through 30 days following the last dose of investigational product. Adverse events will be collected from the date of the first dose through 30 days following the last dose of investigational product.

For a full list of study procedures, including the timing of each procedure, please refer to Section 7 and the Schedule of Assessments (Table 4).

**Statistical Considerations:** There is no formal statistical testing for this study. The analysis of the primary and secondary endpoints will be descriptive in nature.

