# 6.2.3.1.2 Subjects From Study 20110100

For subjects where the last dose of cinacalcet treatment in Study 20110100 and day 1 of Study 20140159 occurs within 14 days, in order to commence dosing, subjects from Study 20110100 will follow the weekly dose adjustment criteria as outlined in Table 2 for age < 2 years and Table 3 for age  $\geq$  2 years. Dose titration cannot occur until week 4.

For subjects with > 14 days and < 1 month between last dose of cinacalcet treatment in Study 20110100 and day 1 of Study 20140159, in order to commence dosing at the initial dose, all subjects from Study 20110100 must meet restart criteria per weekly dose adjustment criteria as outlined in Table 2 for age < 2 years and Table 3 for age  $\geq$  2 years. Dose titration cannot occur until week 4.

- Additionally the phosphorus value within 7 days of day 1 should be:
  - ≥ 5.0 mg/dL (1.25 mmol/L) if age is < 1 year

  - $\ge 4.5 \text{ mg/dL} (1.13 \text{ mmol/L}) \text{ if age is } \ge 1 \text{ year}$

For subjects with > 1 month between last dose of cinacalcet treatment in Study 20110100 and day 1 of Study 20140159, in order to commence dosing, subjects from Study 20110100 must have:

- ionized calcium prior to initiation of treatment on day 1 in this study
  - $\ge 1.13 \text{ mmol/L}$  if age is < 2 years
  - ≥ 1.05 mmol/L if age is ≥ 2 years
- iPTH value ≥ 300 pg/mL within 7 days of day 1
- corrected calcium value within 7 days of day 1
  - ≥ 9.4 mg/dL if age is < 2 years

  - $\ge 8.8 \text{ mg/dL}$  if age is  $\ge 2 \text{ years}$
- phosphorus value within 7 days of day 1
  - ≥ 5.0 mg/dL (1.25 mmol/L) if age is < 1 year

  - ≥ 4.5 mg/dL (1.13 mmol/L) if age is ≥ 1 year

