#### CONFIDENTIAL

# Page 30 of 79

For subjects with  $\leq$  14 days between the last dose of cinacalcet in Study 20110100 and Study 20140159 day 1, subjects will continue the same dose of cinacalcet they received at the completion EOIP visit or early termination visit at Study 20110100 termination and follow the weekly dose adjustments outlined in Table 2. Dose titration cannot occur until week 4. If subjects from the Study 20110100 are on a dose withhold at day 1 of Study 20140159, the iPTH and cCa restart values (iPTH > 150 pg/mL and cCa > 9.0 mg/dL) must be reached prior to resuming cinacalcet in the Study 20140159.

Dose adjustments for subjects receiving cinacalcet will be assessed at each weekly visit during the treatment period. The daily dose of cinacalcet may only be increased at monthly titration visits (week 4, 8, 12, 16, 20, and 24); it can't be increased at any other time during the treatment period. At all weekly visits (including week 4, 8, 12, 16, 20, and 24), the dose may be maintained, reduced or withheld based upon the criteria in Table 2.

If any of the criteria for dose withholding are met at any time during the trial, including between scheduled study visits (ie, unscheduled), the dose of cinacalcet is to be withheld until all of the following criteria are met:

- central laboratory corrected calcium value is >9.0 mg/dL
- iPTH is >150 pg/mL
- ionized calcium is >1.13 mmol/L
- subject has no symptoms of hypocalcemia
- subject doesn't have any ongoing adverse event(s) which warrant withholding of cinacalcet.

If a subject dose is being withheld, ionized calcium levels should be assessed weekly until an ionized calcium of >1.13 mmol/L is obtained, at which point, cCa and iPTH should be assessed by the central laboratory.

Once all the restart criteria above are met, cinacalcet may be restarted at one PSD below the previous dose received. Subjects receiving the lowest PSD (1 mg) who require a dose reduction will have their dose withheld until the criteria for maintaining or increasing the dose are met, at which time they will restart dosing at 1 mg/day.

If subjects require temporary administration of concomitant medications that are known to prolong the QTc interval, are CYP3A4 inhibitors, or are CYP2D6 substrates, the administration of IP is to be withheld. The dose may be restarted at one PSD below the previous dose once the treatment with the concomitant medication has completed and all of the restart criteria above are met.

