Page 32 of 79

If IP has been withheld or missed for more than 14 days, the subject will resume dosing at the starting dose level (initial dose in parent Studies 20130356 or 20110100) once all restart criteria are met.

If any of the criteria for dose decrease are met between scheduled study visits, the dose of cinacalcet is to be suspended until the next visit at which time the dose will be decreased per dose adjustment procedures of that visit.

CONFIDENTIAL

	Monthly Dose Titration Visit Rules (Weeks 4, 8, 12, 16, 20, 24)				Weekly Dose Adjustment Visit Rules (Weeks 1, 2, 3, 5, 6, 7, 9, 10, 11, 13, 14, 15, 17, 18, 19)			Dose Withholding for Safety at Any Time (Monthly, Weekly or Unscheduled)
	↑ one PSD	Maintain Dose	↓ one PSD**	withhold*	Maintain Dose	↓ one PSD**	withhold*	withhold*
	(if all c riteria met)	(if al l criteria met)	(if any criteria met)	(if any criteria met)	(if al l criteria met)	(if any criteria met)	(if any criteria met)	(if any criteria met)
Corrected Calcium (central laboratory)	≥ 9.0 mg/dL	≥ 9.0 mg/dL	≥ 8.6 - < 9.0 mg/dL	< 8.6 mg/dL	≥ 9.0 mg/dL	≥ 8.6 - < 9.0 mg/dL	< 8.6 mg/dL	< 8.6 mg/dL
	(≥ 2.25 mmol/L)	(≥ 2.25 mmol/L)	(≥ 2.15 - < 2.25 mmol/L)	(< 2.15 mmol/L)	(≥ 2.25 mmol/L)	(≥ 2.15 - < 2.25 mmol/L)	(< 2.15 mmol/L)	(< 2.15 mmol/L)
lonized Calcium	≥ 1.13 mmol/L	≥ 1.13 mmol/L	≥ 1.08 - < 1.13 mmol/L	< 1.08 mmol/L	≥ 1.13 mmol/L	≥ 1.08 - < 1.13 mmol/L	< 1.08 mmol/L	< 1.08 mmol/L
Total Calcium (local aboratory)	Not Applicable	< 8.6 mg/dL (< 2.15 mmol/L)	Not Applicable	< 8.6 mg/dL (< 2.15 mmol/L)	< 8.6 mg/dL (< 2.15 mmol/L)	Not Applicable	< 8.6 mg/dL (< 2.15 mmol/L)	< 8.6 mg/dL (< 2.15 mmol/L)
PTH	≥ 300 pg/mL 31.8 pmol/L)	≥ 150 - < 300 pg/mL (≥ 15.9 - < 31.8 pmol/L)	≥ 100 - < 150 pg/mL (≥ 10.6 - < 15.9 pmol/L)	< 100 pg/mL (≥ (< 10.6 pmol/L)	≥ 150 - < 300 pg/mL (≥ 15.9 - < 31.8 pmol/L)	≥ 100 - < 150 pg/mL (≥ 10.6 - < 15.9 pmol/L)	< 100 pg/mL (< 10.6 pmol/L)	< 100 pg/mL (< 10.6 pmol/L)
Symptoms of Hypocalcemia	None	None	N/A	Yes	None	N/A	Yes	Yes
Other AE that warrants IP dose withhold	None	None	N/A	Yes	None	N/A	Yes	Yes

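### Protocol 3.1.2 and SAP 3.1.2 let children under 2 continue cinacalcet at corrected calcium ≥ 8.8 mg/dL, but Table 2, which governs their dosing, maintains the dose only at ≥ 9.0 mg/dL

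*Protocol*

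**What the plan says.** Protocol 3.1.2 covers subjects from Study 20110100. It lets them continue cinacalcet on day 1 if screening iPTH is at least 150 pg/mL and cCa reaches an age-specific limit. For the youngest, the limit is "8.8 mg/dL (age < 2 years of age) or cCa is"; the sentence goes on to give 8.4 mg/dL for age 2 and over. SAP 3.1.2 carries the same numbers. Protocol 3.1.2 then adds: "Cinacalcet dosing will follow the dose titration, dose withhold, and restarting rules defined in Section 6.2.3.1.2".

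Section 6.2.3.1.2 states the rule for children with no more than 14 days since their last dose. To commence dosing they "will follow the weekly dose adjustment criteria as outlined in Table 2 for age < 2 years", or Table 3 from age 2. Section 6.2.3.1.2.1 says that, under age 2, "subjects will continue the same dose of cinacalcet they received at the completion EOIP visit" and that the Table 2 weekly adjustments then apply.

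Table 2 maintains the dose at cCa ≥ 9.0 mg/dL, reduces one protocol-specified dose at "≥ 8.6 - < 9.0 mg/dL", and withholds below 8.6 mg/dL. At the bottom of the dose ladder a reduction is not possible: "Subjects receiving the lowest PSD (1 mg) who require a dose reduction will have their dose withheld until the criteria" for maintaining or increasing are met.

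The synopsis says site staff calculate doses, which are then "confirmed by the interactive voice response/interactive web response (IVR/IWR) system following the titration tables in Section 6".

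**The concern.** A site that reads 3.1.2 on its own would keep a child under 2 on cinacalcet at a cCa of, say, 8.9 mg/dL. Table 2 requires a one-step reduction at that value, or a withhold if the child is on 1 mg. Two parts of the protocol therefore give different instructions for the same blood result.

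This is a calcium limit in the youngest group, which has the tightest calcium limits in the protocol. Hypocalcemia is the main named risk: Section 2.4 reports a pediatric death in the presence of severe hypocalcemia in which a role of cinacalcet could not be excluded.

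**Working it through.** No sample size or error rate is involved. The check sets the cCa limits side by side (all in mg/dL).

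**Step 1. Continuation figure against the weekly maintain limit.**

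| Continuing group | Section 3.1 figure | Weekly maintain limit | Difference |
|---|---|---|---|
| 20130356 cinacalcet arm | 8.4 (3.1.1) | 8.4 (Table 1) | 0 |
| 20110100, age ≥ 2 years | 8.4 (3.1.2) | 8.4 (Table 3) | 0 |
| 20110100, age < 2 years | 8.8 (3.1.2) | 9.0 (Table 2) | 9.0 − 8.8 = 0.2 |

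The 8.8 required of the 20130356 standard-of-care arm is a limit for starting cinacalcet, so it is not part of this comparison.

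**Step 2. Under-2 limit minus the limit for age 2 and over, within Study 20110100.**

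| Cut-point | < 2 years | ≥ 2 years | Difference |
|---|---|---|---|
| Withhold below (Tables 2, 3) | 8.6 | 8.0 | 0.6 |
| Maintain from (Tables 2, 3) | 9.0 | 8.4 | 0.6 |
| Restart above (6.2.3.1.2.1, 6.2.3.1.2.2) | 9.0 | 8.4 | 0.6 |
| Commence after > 1 month off drug (6.2.3.1.2) | 9.4 | 8.8 | 0.6 |
| Continue on day 1 (3.1.2) | 8.8 | 8.4 | 0.4 |

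Only the 3.1.2 pair breaks the pattern, and 8.4 + 0.6 = 9.0 restores it. Table 2's molar units support its own figures: 9.0/2.25 = 4.0 and 8.6/2.15 = 4.0, the same ratio as 8.4/2.1 = 4.0 in Tables 1 and 3. The misprint is therefore more likely in 3.1.2 than in Table 2.

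**Step 3. Where the two rules differ for a child under 2.**

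- 8.8 to < 9.0: 3.1.2 alone says continue; Table 2 says reduce one step (withhold if on 1 mg).
- 8.6 to < 8.8: the 3.1.2 condition is not met; Table 2 says reduce one step. Here 3.1.2 is the stricter.
- Below 8.6 and from 9.0 upward: no disagreement on cCa.

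**Step 4. Who is affected.** Only under-2s with at most 14 days since the last dose. Study 20110100 has 24 weeks of treatment and an end-of-study visit at week 26, so full completers are 26 − 24 = 2 weeks = 14 days off drug, right at the limit. The rest are children who enter when that study is terminated. SAP 3.2 plans 30 subjects from it, spanning 28 days to < 6 years, and the documents give no under-2 count.

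The number on 1 mg cannot be derived either. The extension's starting rule of 0.20 mg/kg/day, rounded down to an available dose, gives 0.20 × 7 kg = 1.4, so 1 mg; 0.20 × 12.4 kg = 2.48, so 1 mg; and 0.20 × 12.5 kg = 2.5 mg. That rule applies only after more than 14 days off drug. Continuing children carry over their last dose.

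**Step 5. Can Table 2 stand as the sole reference?** Three entries differ from the sister tables.

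- The weekly maintain cell for iPTH reads "≥ 150 - < 300 pg/mL (≥ 15.9 - < 31.8 pmol/L"), against ≥ 150 pg/mL in Tables 1 and 3. The weekly columns cover < 100 (withhold), 100 to < 150 (reduce) and 150 to < 300 (maintain). A child at ≥ 300 with no calcium or safety trigger fits none of them.
- Local total calcium < 8.6 mg/dL is printed under both maintain columns, where every criterion must hold, and also under withhold. Tables 1 and 3 show not applicable under maintain.
- The weekly heading lists 15 weeks, ending at week 19. Table 1 lists 21, so 21 − 15 = 6 are missing: weeks 21, 22, 23, 25, 26 and 27.

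**The case against.** The strongest reply is that the protocol already settles the matter. Section 3.1.2 defers to the dosing section, 6.2.3.1.2 states the commencing rule outright, and the interactive system confirms doses from the Section 6 tables. The inclusion criteria for Study 20110100 subjects set no cCa limit, so enrolment is unaffected. All of this stands: a careful reader would apply Table 2, and 8.8 is a stray number rather than a competing rule. It limits the harm but does not make the number right. Site staff calculate the dose first, and the documents do not show how the system was programmed for day 1.

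A second reply is that continuing treatment need not mean continuing at the same dose, so a reduced dose between 8.8 and 9.0 would still be continuation. On that reading the only direct clash in the band is a child on 1 mg. But Table 2 allows reduced dosing down to 8.6, so 8.8 is still wrong (8.8 − 8.6 = 0.2). The 8.4 figures for the other two groups would then also miss their tables' lower limit of 8.0, by 0.4. The same-dose reading fits both other groups exactly. On neither reading does 8.8 match a Table 2 boundary.

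A third reply is that the Table 2 faults are harmless. Section 6.2.3.1.2.1 bars weekly increases, so a child at iPTH ≥ 300 with no other trigger would be maintained by default. It applies the table at all weekly visits, and the any-time withhold column covers the unlisted weeks. Where local calcium sits under two actions, withholding is the safer one. These points hold for a sensible reader, but a table that the text relies on should not need that repair.

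**Conclusion.** The inconsistency is real and sits in current protocol text. The under-2 continuation limit is 0.2 mg/dL below the Table 2 maintain limit, against no difference in the two other continuing groups. It is a wrong dosing threshold, and a minor one. Every value between 8.8 and 9.0 is above the withhold limit of 8.6, ionized calcium is checked on day 1 and weekly, and cCa is redrawn at week 1. No endpoint or analysis uses the figure; in the SAP it is background text.

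That 9.0 is the intended value is an inference from the consistent 0.6 offset, the agreement in the other groups and Table 2's units. The sponsor's medical lead should confirm it. The number of children affected cannot be given from the documents.

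**What to change.** - Change 8.8 to 9.0 mg/dL for age under 2 in protocol 3.1.2 and SAP 3.1.2, once the sponsor's medical lead confirms the intended figure.
- State in 3.1.2 that the tables in Section 6.2.3.1.2 govern dosing.
- Check the interactive dosing system's specification against the corrected rule.
- If the numbers in 3.1.2 are replaced by a cross-reference instead, first correct Table 2: weekly maintain iPTH to ≥ 150 pg/mL, local total calcium to not applicable under both maintain columns, and the weekly heading extended to weeks 21–23 and 25–27.

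The cost is a one-line correction in each document, a clarification memo to sites and a system check, with a few more table cells if Table 2 is corrected at the same time. No additional procedures are needed.

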#### 3.2 Number of Sites

This study will be conducted at approximately 60 sites in North America, Europe, Russia, Latin America, and Australia.

#### 3.3 Number of Subjects

Participants in this clinical investigation shall be referred to as "subjects".

This study is open to subjects who complete the 20-week treatment period or reach study termination in Study 20130356 or the week 26 End of Study visit or reach study termination in Study 20110100. There may be up to 78 subjects enrolled in this study.

Page 20 of 79

# 3.4 Replacement of Subjects

Subjects who are withdrawn or removed from treatment or the study will not be replaced.

# 3.5 Estimated Study Duration

# 3.5.1 Study Duration for Subjects

The total duration for this study is 32 weeks; a 28-week treatment period and 4-week safety follow-up period.

# 3.5.2 End of Study

The end of study is the primary completion date. This is defined as the time when the last subject is assessed or receives an intervention for the purposes of final collection of data.

